3. PROTOCOL SYNOPSIS

[figure not shown]
Test Drugs:	Proellex® (Telapristone Acetate): 6 and 12 mg vaginal capsules and matching placebo
Protocol Number:	ZPV-201
Study Purpose:	To determine the safety and efficacy of two doses of Proellex in premenopausal women with symptomatic (menorrhagia) uterine fibroids confirmed by MRI.
Study Design and Duration of Treatment:	
This study is a phase 2 3-arm-study with two 18-week dosing courses. The study will be conducted in two stages.
 
In the first stage, women will undergo a baseline assessment period with no treatment, until 15-20 days after the start of their second complete menstrual event. During this phase a pictorial blood loss assessment chart will be utilized as well as sanitary products collected from their first menstrual event, for alkaline hematin assay, to determine menstrual blood loss and confirm eligibility.
 
In the second stage, subjects will be randomized into one of 3 arms in a 1-1-1 fashion and receive two 18-week courses of treatment at their randomized dose (6 mg, 12 mg or placebo), separated by an off-drug interval (ODI). The start of the first 18-week course of treatment (Course 1) should commence 15-20 days after the start of their previous menses. Subjects should be instructed to continue vaginal dosing during their menses throughout the study and not to have sex or insert anything in the vagina for at least 1 hour after the capsule is inserted. Once dosing for Course 1 is stopped, subjects will be followed until menses return. The start of the second 18 week course of treatment (Course 2) will commence 15-20 days after the start of their menses following withdrawal of drug after Course 1 has been completed. During the ODI, subjects will continue to record study information in the daily paper diary and PBAC charts as well as collect sanitary products for alkaline hematin assay.
 
After completion of stage 2 dosing (Courses 1 and 2), subjects will be followed through the subsequent 6 menses (recovery menses plus an additional 5 menstrual events), the subject may be offered the opportunity to enroll in an open-label extension study. Subjects who fail to achieve amenorrhea may enroll in the extension study at Visit 19. Amenorrhea is defined as any 28-day period during treatment (not including the ODIs) without a bleeding score >1. Throughout the study women will record study information in the diary, PBAC, and questionnaires as outlined in the study procedures.
 
Subjects will collect and return used sanitary materials for alkaline hematin assay for their first menstrual event during screening, for the recovery menses menses following Course 1, for the 28 days leading

	up to the end of treatment in Course 2, and for the 1 st , 2 nd , 4 th and 6 th menstrual cycles after end of treatment in Course 2.
Subject Population:	The study will enroll healthy adult, pre-menopausal women with confirmed uterine fibroids via MRI and confirmed menorrhagia (>120 mL blood loss per menstrual cycle by historical PBAC assessment, nominal 28 days to ensure a MBL of at least 80 mL by Alkaline Hematin Assay). Subjects with evidence of prior heavy blood loss may be enrolled at the sponsor's discretion.
Number of Subjects:	Up to 45 female subjects, 15 per dose arm
Number of Sites	Approximately 10 sites
Study Duration:	Total participation in the study is approximately 18 months.
Study Endpoints	
The primary endpoint will be:
 
• Percentage of subjects who become amenorrheic after one course of treatment 
Secondary endpoints will be:
 
• Percentage of subjects who become amenorrheic after 2 courses of treatment

	
• Change and percentage change in PBAC score over the course of the study. Specifically comparing the baseline menstrual cycle to the matching end-of-study period leading up to Week 18 and the end of treatment as well as comparing the baseline PBAC to the ODI time periods.• Percentage change in UFSQOL Symptom Severity score (UFS-SSS) comparing Week 18 to Baseline (three month look back) and for the ODI.• Percentage change in the individual UFS-SSS sub scores• Percentage change from baseline in total uterine fibroid volume measured by MRI                   
Statistical Methods:	A Statistical Analysis Plan (SAP) will be developed prior to unblinding of the data that will outline all planned analyses and analysis populations. The first efficacy analysis will be conducted when all subjects complete the first cycle of treatment. A second analysis will summarize the subject's additional treatment cycles which will be conducted after all subjects complete study treatment

	
and follow-up in Stage 2.
 
Summaries for quantitative variables include the sample size, mean, median, standard deviation, minimum, and maximum. Summaries for categorical variables include the number and percent of patients for each outcome. All summaries will be prepared for each treatment group.
 
Continuous efficacy endpoints, such as the change from baseline in the alkaline hematin assay will assess treatment effect using a t-test or appropriate non-parametric technique. Pairwise comparisons between treatment groups will also be conducted with the same methods. Other continuous efficacy variables will be treated similarly. The percentage of subjects becoming amenorrheic within each treatment and dose group will be compared by Chi-square test or appropriate non-parametric method.
 
Safety and tolerability will be assessed by evaluating physical exams, colposcopy findings and reported AEs as well as changes in values from baseline of clinical chemistry variables, hematology variables, hormone variables, and liver function variables. No formal hypothesis testing will be performed to compare the treatment groups. For the quantitative physical exam variables, laboratory variables and bone mineral density the statistical significance of the change from baseline to each of the post-baseline visits will be determined using a paired t-test.

--	--

[figure not shown]

1. Any LFT >ULN will be repeated.

Subjects must be discontinued if any of the following occur:

- ALT or AST >8xULN
- ALT or AST >5xULN for more than 2 weeks
- ALT or AST >3xULN **and** (TBL >2xULN **or** INR >1.5)
- ALT or AST >3xULN with the appearance of fatigue, nausea, vomiting, right upper quadrant pain or tenderness, fever, rash, jaundice (skin or sclera) and/or eosinophilia (>5%)

Cases of liver transaminases that increase above 3 times the upper limit of normal must be reported as SAEs regardless of whether the SAE criteria specified in [Section 10.1.2](#) are met.

[figure not shown]
[figure not shown]

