7. TRIAL OBJECTIVES AND PURPOSE

The primary objective of this study is to determine the safety and efficacy of two vaginal doses of Proellex administered for up to 2 courses of treatment (18 weeks each), each separated by an Off-Drug Interval (ODI), to premenopausal women with symptomatic uterine fibroids.

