12.2 Statistical and Analytical Plan

A Statistical Analysis Plan (SAP) will be prepared prior to unblinding the data. The first efficacy analysis will be conducted when all subjects complete the first cycle of treatment. A second analysis will summarize the subject's additional treatment cycles which will be conducted after all subjects complete study treatment and follow-up in Stage 2. In this Phase 2 study there will be no statistical corrections for interim analyses or multiple comparisons.

For the statistical analysis at the end of the first course of treatment, only statistical staff will be unblinded. All clinical operations staff and staff at investigative sites will remain blinded until completion of the study.

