12.3 General Statistical Issues

A Statistical Analysis Plan (SAP) will be finalized prior to unblinding the study. For the efficacy variables a last observation forward approach will be used to impute missing data to generate a complete ITT data. If there are no post-baseline efficacy data then a value of no change will be imputed for the missing efficacy measure. Statistical significance will be declared if the two-sided p-value is ≤ 0.05 .

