### **6.3 ADJUSTMENT FOR MULTIPLE COMPARISONS**

No adjustments for multiple comparisons will be made in this study.

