### **6.9.1 Adverse Events (AEs)**

[figure not shown]
Treatment-emergent AEs (TEAEs) are defined as those AEs with an onset date and time equal to or after the start of study medication, or those events in which the onset date and time are before the start of study medication but worsened after the start of study medication. To be conservative, in the case of a missing onset time for an AE, an AE with a start date equal to or after the dosing date will be considered treatment-emergent. AE's with missing onset dates will also be considered treatment-emergent.

[figure not shown]
All TEAEs will be summarized by treatment group. The number of TEAEs as well as the number and percentage of subjects who experienced at least one TEAE will be summarized for each system organ class and each preferred term. The percentage will be based on the number of subjects in a particular treatment group included in the Safety population. Each subject will contribute at most one count per summarization category. TEAEs potentially related to study medication, serious TEAEs, and TEAEs leading to withdrawal will be summarized in a similar manner.

If a subject has more than one AE that codes to the same preferred term, the subject will be counted only once for that preferred term. Similarly, if a subject has more than one AE within a system organ class category, the subject will be counted only once for that system organ class category.

TEAEs will also be summarized by maximum severity and by strongest relationship to treatment within each treatment group. Serious adverse events (SAEs) will be tabulated and listed in a

manner similar to TEAEs. A listing of all AE data will be provided to supplement the tabulated results.

**Repros Therapeutics Inc.  
[name]  
[name]**

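### The only safety p-values in the legible plan are within-arm paired t-tests against baseline, which cannot separate a drug effect from change shared with placebo

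*Protocol*

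**What the plan says.** The statistical methods entry of the protocol synopsis (section 3) makes two linked choices for safety. It states: "No formal hypothesis testing will be performed to compare the treatment groups". Then, for quantitative physical-exam variables, laboratory variables and bone mineral density, it states that "the statistical significance of the change from baseline to each of the post-baseline visits will be determined using a paired t-test".

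The significance rule is general. Protocol 12.3 reads "Statistical significance will be declared if the two-sided p-value is" at most 0.05, and SAP 6.1 repeats it. Protocol 12.2 adds that "there will be no statistical corrections for interim analyses or multiple comparisons", and SAP 6.3 agrees: "No adjustments for multiple comparisons will be made in this study".

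Placebo is not absent from safety reporting. The synopsis says "All summaries will be prepared for each treatment group", and SAP 6.9.1 says "All TEAEs will be summarized by treatment group".

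Safety is not a side issue. Protocol section 7 opens: "The primary objective of this study is to determine the safety and efficacy of two vaginal doses of Proellex". SAP section 2 gives the study purpose as a comparison of the two doses with placebo.

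Under SAP 6.9, only the adverse-event part is legible. The laboratory and bone-density parts, and the visit schedule for these measurements, cannot be read.

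**The concern.** A paired t-test asks whether the mean in one arm moved from its own baseline. It does not ask whether the drug moved it. Any influence that acts on all three arms contributes to the result. Candidates here are the passage of time over about 18 months of participation, differences in cycle phase between baseline and later visits, and regression to the mean after women with clinically significant screening abnormalities are excluded (protocol 8.3.2). How strongly each acts depends on the sampling schedule.

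Purely descriptive safety reporting would be defensible at 15 per arm. This plan goes further and attaches significance to a contrast that does not isolate the drug, while withholding it from the one that does. In the same synopsis entry, the efficacy endpoints do get pairwise comparisons between arms.

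The risk lies in interpretation. A change common to all arms can be reported as significant in an active arm. By chance, it can also be significant in an active arm and not in placebo, which looks like a drug effect. Running such tests on every variable at every visit without correction adds chance findings.

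**Working it through.** The documents give no test count, error rate or power for the safety tests, so there is no stated figure to reproduce.

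**Inputs from the documents**
- Subjects per arm: n = 15 (protocol 12.1, SAP 3.2).
- Arms: 6 mg, 12 mg and placebo, randomised 1:1:1 (synopsis).
- Level: two-sided 0.05, no correction (protocol 12.2 and 12.3; SAP 6.1 and 6.3).

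**Assumptions**
- Normally distributed changes, equal SD in each arm, 15 complete pairs per arm.
- Shared drift d of 0.25, 0.5 or 0.75 SD of change, with no drug effect.
- 15-30 variables and 4-12 post-baseline visits. Neither count is legible.

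**Step 1: drift shared by all arms.** The paired t statistic has n − 1 = 14 degrees of freedom and noncentrality d√15. Let p be its two-sided rejection probability. The arms are independent, so a given active arm is significant while placebo is not with probability p(1 − p). The chance that at least one of the two active arms shows this pattern is (1 − p)[1 − (1 − p)²].

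| Drift d (SD of change) | Significant within an arm, p | This active arm significant, placebo not | At least one active arm significant, placebo not | Direct comparison with placebo |
|---|---|---|---|---|
| 0.25 | 0.147 | 0.147 × 0.853 = 0.13 | 0.853 × 0.273 = 0.23 | 0.05 |
| 0.50 | 0.438 | 0.438 × 0.562 = 0.25 | 0.562 × 0.684 = 0.38 | 0.05 |
| 0.75 | 0.771 | 0.771 × 0.229 = 0.18 | 0.229 × 0.947 = 0.22 | 0.05 |

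The last column stays at 5% because a common drift cancels in the difference between arms.

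**Step 2: chance findings if nothing changes over time.** This is a different null from step 1, and the two should not be added together. The expected number in the two active arms is 0.05 × variables × visits × 2.
- Low end: 0.05 × 15 × 4 × 2 = 6.
- High end: 0.05 × 30 × 12 × 2 = 36.

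Correlation between tests leaves the expected count unchanged but lowers the chance of seeing at least one. For example, assume 20 variables at 6 visits, or 120 tests per arm. The chance of at least one significant result in an arm is 99.8% with independent tests. In simulation it is 96% with correlation 0.3 between variables and 0.5 between visits, and 79% with 0.5 and 0.7.

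**Step 3: precision of the between-arm estimate.** For an unadjusted difference with 15 per arm, the 95% confidence interval half-width is t(0.975; 28) × √(2/15) = 2.048 × 0.365 = 0.75 SD of change. A between-arm test would need a true difference of about 1.06 SD for 80% power.

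**The case against.** A reader might infer that the placebo arm is never used for safety. The documents do not support that. By-arm summaries are planned for all quantitative data and for adverse events, so a rise in every arm would be visible in the placebo column. What holds is narrower: placebo is left out of every safety significance test that can be read.

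The governing text may also be out of sight. The paired tests appear in a synopsis sentence, the synopsis leaves the full set of analyses to the SAP, and the SAP's laboratory part is not legible. Nobody can say from these documents whether the SAP keeps, changes or drops them. That limits the point to the protocol as written but does not remove it.

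A count over all three arms would be 9-54 chance findings on the same assumptions. One third of those fall in the placebo arm, where they cannot be false drug signals. Hence the figure of 6-36, which still rests on assumed panel sizes.

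A reader might also infer that a liver signal could be passed over because a mean change was not significant. The documents do not support that either. Liver safety rests on individual thresholds, discontinuation criteria and mandatory reporting (synopsis; protocol 10.1.2 and 10.1.3), and no legible decision rule uses these p-values.

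Finally, the within-arm test is the more sensitive one: it reaches 80% power at about 0.78 SD, against 1.06 SD between arms. That is true, but it is sensitive to change from any cause. Declining formal between-arm safety tests in a phase 2 trial of this size is reasonable. It does not justify significance statements on within-arm change.

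**Conclusion.** The point holds for the protocol text. The stated safety tests put significance on a contrast that cannot distinguish drug effect from change common to all arms. With 15 per arm and no drug effect, a shared drift of 0.5 SD is significant within an arm about 44% of the time, and a given active arm is significant while placebo is not about 25% of the time. A direct comparison with placebo would flag 5%. These rates depend on the assumed drift; the range from 0.25 to 0.75 SD gives 15% to 77% and 13% to 25% respectively.

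Separately, if there is no change over time, about 6-36 chance findings are expected in the two active arms, given 15-30 variables and 4-12 visits. Those two counts are assumptions, so this range shows scale only.

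This is a worthwhile, low-cost improvement to the safety analysis. It is not evidence that placebo data are ignored or that individual safety monitoring is weakened.

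**What to change.** Replace the within-arm p-values with the active-minus-placebo difference in change from baseline, for each dose, estimated by ANCOVA with the baseline value as covariate. Report 95% confidence intervals without significance claims. Do this at the end of Course 1 and the end of Course 2, where the variable is measured. Naming these two time points and making no significance claims also deals with multiplicity. Changing the contrast alone would not, since a between-arm test of everything at every visit would still flag about 5% of true nulls.

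Keep within-arm changes, other visits and post-treatment follow-up as descriptive summaries by arm. Follow-up should not carry a formal contrast. Women who do not achieve amenorrhea may enter the extension study at Visit 19 (synopsis; protocol 8.2.1 and 8.2.3), so those who remain are selected on the efficacy outcome, and that selection may differ by arm.

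The SAP should state the method for laboratory, physical-exam and bone-density data so that it agrees with the synopsis. If it already departs from the paired tests, only the synopsis wording needs to change.

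The cost is revised wording and table programming, with no new data. The drawback is wide intervals, with a half-width of about 0.75 SD of change before baseline adjustment; that is the precision this sample size gives. The individual liver thresholds and serious adverse event rules are unaffected.

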5. LIST OF ABBREVIATIONS

AE	Adverse event
C_{avg}	Average concentration
C_{max}	Maximum concentration
CRF	Case report form
DHEA	Dehydroepiandrosterone
dL	Deciliter
ECG	Electrocardiogram
FSH	Follicle-stimulating hormone
GCP	Good Clinical Practice
GnRH	Gonadotrophin releasing hormone
g	Grams
hCG	Human chorionic gonadotrophin
ICH	International Conference on Harmonization
IGF-1	Insulin-like growth factor-1
IRB	Institutional Review Board
IND	Investigational new drug
IUD	Intra-uterine device
kg	Kilogram(s)
LD_{50}	Median lethal dose
LH	Luteinizing hormone
LSC	Least Significant Change
m	Meters
MBL	Menstrual Blood Loss
mg	Milligram(s)
mL	Milliliter
ng	Nanograms
OC	Oral Contraceptive
ODI	Off-Drug Interval
PBAC	Pictorial Blood Loss Assessment Chart
PCOS	Polycystic Ovarian Syndrome
PK	Pharmacokinetic
RBC	Red blood cell
SAE	Serious adverse event
UFSQOL	Uterine Fibroid Symptom Quality of Life Survey
UFS-SSS	Uterine Fibroid Symptom Quality of Life Survey Symptom Severity Score (first 8 questions)
WBC	White blood cell

6. BACKGROUND INFORMATION

6.1 Rationale for Current Study

Repros believes telapristone offers the potential to provide significant symptomatic relief to women that suffer from a variety of reproductive disorders in which progesterone may be implicated.

Based on recent findings in rabbit and dog studies the sponsor believes vaginal administration of Telapristone will bypass the liver, achieve higher local concentrations and better effects in utero while significantly reducing safety margin.

[REDACTED]

[figure not shown]
[REDACTED] Typically women are dosed for 4 months (120 days) after which time the drug is withdrawn to allow for menses to return. Once menses has occurred women may resume treatment for another dosing period. In this fashion the drug can be used to control the symptoms of endometriosis and fibroids until the onset of menopause.

[figure not shown]
6.2 Non-Clinical Data

[REDACTED]

[REDACTED]

[REDACTED]

[figure not shown]
Endometrial Proliferation

BioQual also used a scoring system that assessed several uterine sections from the five rabbits in each dose group. [REDACTED]

[REDACTED]

[REDACTED]

[figure not shown]
[figure not shown]
[figure not shown]
[REDACTED]

[REDACTED]

6.3 Clinical Data/Human Experience

[figure not shown]
In addition to the preclinical studies, a Phase I/II study of orally administered Proellex in pre-menopausal women with symptomatic leiomyomata has been completed. The objectives of this study were to test the safety, efficacy, and pharmacokinetics of three doses of Proellex (12.5 mg, 25 mg, and 50 mg) administered as a once daily dose for 90 days, with study visits at one-month intervals. The safety and effectiveness of Proellex was compared to placebo and the active control leuprolide acetate for depot suspension (Lupron Depot). At the conclusion of this study, exploratory analyses showed statistically significant efficacy differences between treatment groups (overall and pair-wise).

6.4 Safety Data

**FDA Guidance For Liver Enzyme
Elevation Characterization as SAE**

- 1. LFTs \geq 8 x ULN
- 2. LFTs \geq 5 x ULN for 2 consecutive weeks
- 3. LFTs \geq 3 x ULN + Bilirubin 2 x ULN
- 4. LFTs \geq 3 x ULN + clinical signs or symptoms (nausea; jaundice; etc.)

6.5 Data From ZPV-200

This study included an initial two week exposure of vaginal administration of 12mg telapristone acetate in six women with uterine fibroids to determine the length of time it takes for the drug to reach steady state and the overall systemic exposure of both the parent compound and the primary metabolite. The purpose of this first cohort was to determine whether the systemic exposure of 12mg vaginal for both the parent molecule and primary metabolite was less than that which had been safely tested in the previously completed low dose oral study ZP-204.

[REDACTED]

[REDACTED]

[REDACTED]

[REDACTED]

[REDACTED]

[REDACTED]

[REDACTED]

[REDACTED]

6.6 Ethical Conduct of the Study

This trial will be conducted in strict compliance with the protocol and all applicable FDA regulations and GCP guidelines to insure Good Clinical Practice standards. IntegReview, [name], will serve as an Institutional Review Board (IRB) for clinical sites who will accept their review.

7. TRIAL OBJECTIVES AND PURPOSE

The primary objective of this study is to determine the safety and efficacy of two vaginal doses of Proellex administered for up to 2 courses of treatment (18 weeks each), each separated by an Off-Drug Interval (ODI), to premenopausal women with symptomatic uterine fibroids.

